1.4.1 Interventions and Comparators

N-of-1 Trial arm: Participants will use the Eureka mobile application and AliveCor device to execute at least one N-of-1 trial with the goal of identifying and better controlling their AF triggers. Each N-of-1 trial will last a total of 6 weeks and will include up to 3 periods of trigger exposure and 3 periods of trigger elimination with each exposure/elimination period lasting 1 week. Participants will be randomly assigned to start their trial with a period of either trigger exposure or elimination. During each N-of-1 trial, participants will track daily AF duration and severity, daily mood and sleep quality, daily AliveCor tracings and daily trigger exposure. At the end of each trial, participants will be able to review their trial results which will include visualizations of their daily AF symptom and trigger tracking over time. After completing a trial, participants will be instructed to implement any lifestyle changes they deem appropriate based on what they learned from the results of their trial. Participants will implement these changes for a period of 4 weeks during which they will continue to track AF episode duration and severity via the app. At the end of the 4-week lifestyle change period, participants will complete the Atrial Fibrillation Effect on QualiTy of Life survey (AFEQT) (Appendix A) and will then have the option of testing another trigger or ending their study participation.

Symptom Surveillance arm: Participants will use the Eureka app and AliveCor device to record daily AF duration and severity, daily AliveCor readings and daily mood and sleep quality for a period of 10 weeks. Participants will be able to visualize their AF, sleep and mood data in real time and will receive a weekly summary of their data via the Eureka app.At the end of the 10-week data tracking period, participants will complete the AFEQT survey and will then have the option of either ending their study participation or crossing over to the N-of-1 trial arm to test their triggers.

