1.8 Safety and Adverse Events (AE)

1.8.1 Adverse Event Reporting

Participants will receive monthly prompts via the application about the following things: hospitalizations (AF, emergency department, cerebrovascular event, myocardial infarction or heart failure), antiarrhythmic medication changes and ablation plans.

We will share reports with the DSMB outlining the results of the above survey.

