1.8.2 Data and Safety Monitoring Board

Although randomization to N-of-1 trials versus symptom surveillance (data tracking) is low risk, we will form a DSMB to ensure the safety of participants. This board will be comprised of a patient, a cardiac electrophysiologist, and a statistician from outside the research groups or institutions of the study personnel otherwise involved in the project. They will meet prior to

implementation of the study to review the safety of a near-final AF-specific N-of-1 platform. They will meet again after 100 patients are enrolled and again after 350 patients are enrolled.

An analyst will prepare summary statistics of results collected prior to the second and third meetings. The DSMB will review study progress and any adverse events that have been reported by patients. The DSMB will also discuss trouble around retention, compliance, protocol violation and recruitment issues. The DSMB will have the authority to stop the study for safety reasons or to alter it if needed. Because the study is expected to be low risk, patients may actually benefit from study participation, and specific subgroups (e.g., those in whom N-of-1 studies identify a trigger), may yield important results, the DSMB will not perform any interim analyses for efficacy or consider stopping the study early for futility. In addition, all potential participant data obtained by the study investigators will be monitored on an ongoing basis to ensure compliance, to provide quality assurance (QA), and to obtain metrics for quality improvement.

See Appendix C for DSMB Charter

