N-of-1 Trial arm: Patients will use the Eureka mobile application and AliveCor device to execute at least one N-of-1 trial with the goal of identifying and better controlling their AF triggers. Each N-of-1 trial will last a total of 6 weeks and will include up to 3 periods of trigger exposure and 3 periods of trigger elimination with each exposure/elimination period lasting 1 week. Patients will be randomly assigned a sequence of trigger exposure and elimination periods such that they receive each treatment in each two-week block. During each N-of-1 trial, patients will track daily AF duration and severity, daily mood and sleep quality, daily AliveCor tracings and daily trigger exposure. At the end of each trial, patients will be able to review their trial results which will include visualizations of their daily AF symptom and trigger tracking over time. After completing a trial, patients will be instructed to implement any lifestyle changes they deem appropriate based on what they learned from the results of their trial. Patients will implement these changes for a period of 4 weeks during which they will continue to track AF episode duration and severity via the app. At the end of the 4-week lifestyle change period, patients will complete the Atrial Fibrillation Effect on Quality of Life survey (AFEQT) (Appendix A) and will then have the option of testing another trigger or ending their study participation.

Symptom Surveillance arm: Patients will use the Eureka app and AliveCor device to record daily AF duration and severity, daily AliveCor readings and daily mood and sleep quality for a period of 10 weeks. Patients will be able to visualize their AF, sleep and mood data in real time and will receive a weekly summary of their data via the Eureka app. At the end of the 10-week data tracking period, patients will complete the AFEQT survey and will then have the option of either ending their study participation or crossing over to the N-of-1 trial arm to test their triggers.

Primary Study Aim:

To test the comparative effectiveness of N-of-1 trials vs. data tracking alone to identify and eliminate individual level triggers and reduce AF frequency and severity as measured by the atrial fibrillation quality of life scale (AFEQT)

Secondary Aims:

- Using individual N-of-1 trials, identify modifiable exposures that increase the risk for an AF episode on an individual-level.

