4.1 Measures

Data that will be collected during the study are detailed in Table 2:

Construct	Measure(s)	Categorization	Timing	Source	
Primary Outcome (comparing N-of-1 group to data tracking group)					
Atrial fibrillation quality of life	AFEQT score	Integer (20-140). Survey includes 20 questions 1-7	Baseline and 10 weeks	Eureka app	
		score for each			
Primary Outcomes	(for individual-level	N-of-1 trials within th	e N-of-1 group)	Γ	
Atrial fibrillation	ECG flagged by	1=Yes	Daily and whenever	AliveCor app	
device	algorithm	U=INO	a symptomatic		
Atrial fibrillation	Patient report	1=Yes 0=No	Daily	Eureka app	
Atrial fibrillation duration	Patient report (hrs and minutes)	Integer 0-60 hrs, 0-60 min	Daily (queried only if self-reported atrial fibrillation=Yes on that day)	Eureka app	
Atrial fibrillation severity	Patient report	Integer 1-7, ordinal scale 1=least severe	Daily (queried only if self-reported atrial fibrillation=Yes on that day)	Eureka app	
SECONDARY ENDPOINTS					
AliveCor confirmed atrial fibrillation event	Patient reported atrial fibrillation event confirmed	1=Yes 0=No	Daily and whenever a symptomatic episode occurs	AliveCor app and Eureka app	

Table 2

within the N-of-1 group and compared to data tracking in last	by report from AliveCor device			
Count of AF Frequency	The number of patients reported AF episodes during the final month of enrollment	Integer 0-7—count	Daily	Eureka app
Total duration of AF episodes	Total duration of patient reported AF episodes daily during the final month of enrollment	Continuous 0-60 min, 0-24 hours 0= no answer	Daily (only if self-reported atrial fibrillation=Yes on that day)	Eureka app
Average severity of AF episodes	average severity of patient reported AF episodes daily during final month of enrollment	Continuous (range 1-7 using, Ordinal Scale 1=least severe 0= no answer	Daily (only if self-reported atrial fibrillation=Yes on that day)	Eureka app
Safety Measures Emergency room visit	Patient report	1=Yes 2=No 3=Don't know If yes, date and hospital location	Monthly: Reported at 4 & 8 weeks; actual emergency room visits will be categorized by day	Eureka app
Emergency room visit related to atrial fibrillation	Patient report	1=Yes 2=No 3=Don't know	Monthly (queried only if emergency room visit=Yes for that month) Reported at 4 &8 weeks.	Eureka app

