Hospitalization	Patient report	1=Yes 2=No 3=Don't know If yes, date and hospital location	Monthly; actual hospitalizations will be categorized by day reported at 4 and 8 weeks.	Eureka app
Hospitalization related to atrial fibrillation	Patient report	1=Yes 2=No 3=Don't know	Monthly (queried only if hospitalization=Yes for that month)	Eureka app

			Reported at 4 &8	
			weeks.	
Cerebrovascular accident	Patient report	1=Yes 2=No 3=Don't know If yes, date and location diagnosis	Monthly; reported at 4 &8 weeks.	Eureka app
Myocardial infarction	Patient report	made 1=Yes 2=No 3=Don't know If yes, date and location diagnosis made	Monthly; reported at 4 &8 weeks.	Eureka app
Heart failure	Patient report	1=Yes 2=No 3=Don't know If yes, date and location diagnosis made	Monthly; reported at 4 &8 weeks.	Eureka app
MODIFIERS	_			
Age	Patient report	Continuous	Baseline only	Eureka app
Gender Identity	Patient report	1=Woman 2=Man 3=Transgender Woman 4=Transgender Man 5=Genderqueer 6=Another gender identity 7=Decline to state	Baseline only	Eureka app
Sex	Patient report	1=Male 2=Female 3=Prefer not to state	Baseline only	Eureka app
Race	Patient report	1=Black 2=White 3=Asian 4=Native Hawaiian or Pacific Islander 5=American Indian or Alaska Native 6=Some other race 7=Don't know	Baseline only	Eureka app

		8=Prefer not to		
		state		
Hispanic	Patient report	1=Not Hispanic 2=Yes: Mexican, Mexican American or Chicano 3=Yes: Puerto Rican 4=Yes: Cuban 5=Yes: Cuban 5=Yes: Mixed Hispanic, Latino or Spanish Origin 6=Yes: Other Hispanic, Latino, or Spanish Origin 7=Don't know 8=Prefer not to state	Baseline Only	Eureka app
Education level	Patient report	1=No formal schooling 2=Some school, but did not graduate high school 3=High school diploma or equivalent 4=Associate degree 5=Some college 6=Bachelor's degree 7=Master's degree 8=Doctorate 9=Professional doctorate 10=Other 11=Don't know 12=Prefer not to state	Baseline Only	Eureka app
Household income	Patient report	1= Under \$10,000 2= \$10,000 to under \$20,000 3= \$20,000 to under \$30,000	Baseline Only	Eureka App

		4=\$30,000 to		
		under \$40,000		
		5= \$40,000 to		
		under \$50,000		
		6= \$50,000 to		
		under \$75,000		
		7= \$75,000 to		
		under \$100,000		
		8= \$100,000 to		
		under \$150,000		
		9= More than		
		\$150,000		
		10= Don't know		
		11= Prefer not to		
		state		
Household size	Patient report	Integer 0-20	Baseline Only	Eureka app
Hoight	Dationt report	Integer 1 10 ft	Pacolino Only	Euroka ann

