4.4. Safety Endpoints

- 1. **Hospitalization** Days on which any hospitalization occurs together with date and hospital location. This will be recorded from the Eureka app and will be reported monthly by the patient.
- 2. **Hospitalization related to atrial fibrillation** Days on which a hospitalization related to atrial fibrillation occurs together with date and hospital location. This will be recorded from the Eureka app and will be reported monthly by the patient.
- 3. **Emergency department visit** Days on which any emergency department visit occurs together with date and hospital location. This will be recorded from the Eureka app and will be reported monthly by the patient.
- 4. **Cerebrovascular accident** Days on which any cerebrovascular accident occurs together with date and hospital location. This will be recorded from the Eureka app and will be reported monthly by the patient.
- 5. **Myocardial infarction** Days on which a myocardial infarction occurs together with date and hospital location. This will be recorded from the Eureka app and will be reported monthly by the patient.
- 6. **Heart failure** Days on which heart failure occurs together with date and hospital location. This will be recorded from the Eureka app and will be reported monthly by the patient using language from previous HeH surveys.

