5.4.3 Meta-Analysis of N-of-1 Trials

We will conduct separate meta-analyses of each set of N-of-1 trials that test a particular trigger. We expect this will likely be most relevant to the triggers offered in the menu which patients are more likely to try and which were also the most commonly identified triggers in a survey recently sent to 1,000 AF patients. The meta-analyses will use the same Bayesian multilevel methods as those outlined in Aim 1 and will be applied to the outcomes of AF events, duration and severity as well as the safety endpoints listed in Table 2. We will use distribution and link functions appropriate to the scale of each outcome variable. We will calculate the average treatment effect in the group of patients as well as the individual effects adjusted for the other patients.

Patients with AF are particularly interested in whether certain triggers are more likely than others to induce AF. Because patients in this study will be choosing to study different triggers and often will be conducting more than N-of-1 trial, the set of trigger comparisons will form a network of triggers (plus no trigger) that may be analytically compared using methods of network meta-analysis.²⁵ Triggers may then be compared indirectly through the common control using techniques from network meta-analysis. The complicating factor here is that trials done by the same patient will be correlated and it will be necessary to adjust for this correlation in the network meta-analysis model. This can be done in two different ways. The first would be to treat each patient's trials as separate and introduce a common patient effect into a Version 1.0 5/12/17

mixed model. The second would be to combine all the trials for a patient into one trial with several arms, one for each different trigger and one for no trigger that would combine all the results from the no trigger arms. If a patient changed the control (no trigger) arm in a new trial (e.g., by testing two triggers vs. one trigger), then the control arm would be analyzed according to the trigger used. This approach would create multi-arm trials for patients with multiple trials. These would then be analyzed by methods for multi-arm studies in a network meta-analysis.

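### Safety events are queried only at weeks 4 and 8, which does not fit one-week trigger periods or the planned on/off safety analysis, and leaves weeks 9-10 with no listed report

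*Protocol*

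**What the plan says.** **Harm queries.** Protocol 1.8.1 provides for one scheduled query: "Participants will receive monthly prompts via the application about the following things: hospitalizations (AF, emergency department, cerebrovascular event, myocardial infarction or heart failure". SAP Table 2 (section 4.1) fixes the timing. For emergency visits it reads "Monthly: Reported at 4 & 8 weeks; actual emergency room visits will be categorized by day", and for hospitalisation "Monthly; actual hospitalizations will be categorized by day reported at 4 and 8 weeks". Cerebrovascular accident, myocardial infarction and heart failure follow the same schedule. SAP 4.4 also has them reported monthly by the patient and asks for a date and place, for example "Days on which any hospitalization occurs together with date and hospital location".

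**Exposure schedule.** Protocol 1.4.1: "Each N-of-1 trial will last a total of 6 weeks and will include up to 3 periods of trigger exposure", with an equal number of elimination periods, each lasting one week. SAP section 2 randomises the order "such that they receive each treatment in each two-week block". A four-week lifestyle-change period follows, so the study period is 10 weeks.

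**Use of the safety data.** SAP 5.4.1 compares the arms on each safety event as a binary any-event outcome. SAP 5.4.3 adds that the N-of-1 meta-analysis "will be applied to the outcomes of AF events, duration and severity as well as the safety endpoints listed in Table 2". SAP 5.4.1.2 treats days with no reported safety event as event-free. Protocol 1.8.2 states that "we will form a DSMB to ensure the safety of participants", and Protocol 1.8.1 sends the board reports of the monthly survey results.

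**The concern.** Three things do not fit together.

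- **Interval against period.** The condition is assigned week by week, but the participant is asked about harm every four weeks. An event in an early exposure week may be reported only after a later exposure week has begun.
- **Interval against analysis.** SAP 5.4.3 needs every safety event placed in an exposure or elimination week. The only information for this is a date the participant gives up to 28 days afterwards; no check against records is described.
- **Coverage.** The listed reports stop at week 8 of a 10-week period. An event in weeks 9-10 has no listed route into the data, and the missing-data rule would score those days as free of events.

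At stake are timely knowledge of harm during testing, the accuracy of a secondary on/off safety analysis, and complete ascertainment over the comparison period.

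**Working it through.** **Inputs.** Reports at weeks 4 and 8 (SAP Table 2); six one-week periods, three on and three off (Protocol 1.4.1 and 1.5); one of each per two-week block (SAP section 2); a 10-week period. The monthly interval in Protocol 1.8.1 reproduces the SAP times, since two four-week prompts fit in 10 weeks, at weeks 4 and 8. Assumption for steps 1 to 5: the weeks count from the start of testing.

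**1. Exposure weeks completed by week 4.**

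| Sequence rule | Sequences | Exposure weeks done by week 4 |
|---|---|---|
| Two-week blocks (SAP section 2) | 8 | 2 of 3 in all 8 |
| Strict alternation (a reading of Protocol 1.4.1) | 2 | 2 of 3 in both |
| Any 3 of 6 (looser wording of Protocol 1.4) | 20 | 1 in 4, 2 in 12, 3 in 4 |

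**2. Reporting delay.** Events are taken as spread evenly over the six test weeks. Weeks 1-4 are reported at week 4 (mean wait 2 weeks); weeks 5-6 at week 8 (mean wait 3 weeks). Mean = (4 × 2 + 2 × 3)/6 = 14/6 = 2.33 weeks. With end-of-week prompts it is 0.5 week.

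**3. Further exposure before any report.** The 8 block sequences contain 8 × 3 = 24 exposure weeks. The 8 in the first block are followed by the second block's exposure week before the week-4 report: 8/24 = 1 in 3. The second block is reported at its own end, and nothing follows the third. With end-of-week prompts, answered when sent, the count is 0 of 24.

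**4. Misplacement by recalled date.** The documents give no recall error, so a whole-day rounded normal error is assumed. Over 42 days there are 5 week boundaries. Under blocks, the 3 within blocks always change condition and the 2 between blocks do so half the time, giving 4 changes on average. An error of k days, in either direction, crosses a change for 2 × 4 × k of the 84 day-and-direction pairs, that is 8k/84 for small k.

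- SD 0.5 day: P(error of 1 day) = 0.315, so 0.315 × 8/84 = 3.0%; larger errors add less than 0.1 point.
- SD 1 day: 0.484 × 8/84 + 0.121 × 16/84 + 0.012 × 24/84 = 4.6% + 2.3% + 0.3%, about 7%.
- Under strict alternation (5 changes) the figures are about 4% and 9%.

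**5. Uncovered time.** Week 8 is the last listed report, so 10 − 8 = 2 weeks have none. In the N-of-1 arm these are the second half of the four-week lifestyle-change period.

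**6. Dependence on the clock.** SAP 4.2 equates baseline with randomisation, and Protocol 1.5 puts about two weeks of device shipping between randomisation and testing. Counted from randomisation, the reports fall at the end of test weeks 2 and 6. Under blocks the first report then follows one exposure week; mean delay is (2 × 1 + 4 × 2)/6 = 1.67 weeks; the 1-in-3 share is unchanged (now events in the second block); and the uncovered stretch becomes test weeks 7-10. Counting from the start of testing is the more natural reading of a 10-week schedule, but the SAP does not say so.

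**The case against.** The case for leaving the plan alone is substantial, and much of it stands.

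- **The main safety analysis is not touched by misplacement.** Moving an event from an on week to an off week cannot change whether a participant had any event, which is what SAP 5.4.1 compares between arms. A reader might infer that late recall dilutes every harm contrast in the trial. It does not; only the SAP 5.4.3 analysis is exposed. No event rate is given, so the documents do not show that this analysis would be informative even with perfect dates.
- **Dates are collected.** SAP 4.4 asks for date and place, and Table 2 categorises hospitalisations and emergency visits by day. These are memorable events. With a recall SD of 2 days, about 15% of events would be misplaced and an on/off difference would shrink by roughly 30%, but nothing in the documents supports so large an error.
- **The study is not blind to harm between prompts.** AF episodes and ECGs are recorded daily, Protocol 1.8.2 promises ongoing monitoring, SAP 4.6.2 sends reminders by push notification or text message, and SAP 6.2 makes coordinators reachable. It would go too far to say that the study cannot learn of an early admission, or that someone who stops opening the app is never asked. What remains is that none of these is a scheduled question about the listed events, and SAP 6.1 says AF episodes themselves are not a safety concern.
- **Low risk.** The documents justify light monitoring because the exposures belong to ordinary life. That argues against a heavy remedy, not against one short item.
- **Prompts alone protect nobody.** The 0 of 24 in step 3 assumes a prompt answer and someone who sees it. That is fair, and the fix has to include visibility to the study team.

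**Conclusion.** The point holds as a low-cost improvement, not as a flaw in the primary or main safety comparison. The harm query does not match the one-week periods or the SAP 5.4.3 analysis that uses its data. Counted from the start of testing, the first report comes after two of three exposure weeks (under blocks or alternation), and the mean delay is 2.33 weeks against 0.5. One exposure-week event in three is followed by the start of another exposure week before any report. The first two figures change if the clock starts at randomisation; the last does not. Date misplacement is confined to SAP 5.4.3 and probably small, about 3% to 7% of events under an assumed recall SD of 0.5 to 1 day.

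The coverage gap rests on no recall assumption: no listed report reaches weeks 9-10, while SAP 5.4.1.2 counts unreported days as event-free. Unlike misplacement, this can affect the between-arm any-event comparison, because events in that time could be missed in either arm. The documents do not show that it would favour one arm.

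**What to change.** In Protocol 1.8.1 and in SAP Table 2 and 4.4:

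1. Replace the monthly safety prompt with one yes/no gate item covering the listed events, at the end of each week in both arms through week 10. Ask details and date only after a yes.
2. Store the period label (exposure or elimination) with each answer, and use it with the date for on/off assignment in SAP 5.4.3.
3. State the clock anchor for all safety reports.
4. Make a yes visible to the study team on receipt, not only in the report to the DSMB. Any action that follows is for the investigator and the DSMB to define.

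The cost is app configuration, short wording changes in both documents, and one extra brief item per week in an app that already prompts participants daily. The added burden is small and the same in both arms.
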